## **7. STATISTICAL PLAN**

## 7.1 Sample Size Determination

The choice of sample size is based upon a comparison for the primary outcome (secondary procedures) of THA versus HA. All statistical hypotheses will be two-sided. Alpha levels of 0.05 for the primary and 0.01 for the secondary outcomes were chosen. Previous studies have reported secondary procedure rates in hip fracture patients treated with HA that have ranged from 4 to 10% at one year, with a weighted pooled risk of 5.3% (95% CI 3.2 to 8.9%) in a fixed effect meta-analysis, or 4.9% (95% CI 2.6 to 9.2%) using random effects. A pooled estimate from 5 randomized trials comparing THA with HA gave a relative risk of 1.67 (95% CI 0.86 to 3.24,  $p=0.13$ ) (**Table 3a**).

The sample size calculation reflects the proposed approach to the primary analysis, which will use the Cox proportional hazards model. The calculation is based on methods described by Collett (Collett, 1994). The goal is to calculate the required number of patients that will yield a sufficient number of outcome events (secondary procedures) in order to have adequate statistical power for a given size of treatment effect. This was done taking into account the anticipated secondary procedure rates in the HA group, postulated values of the relative risk increase associated with THA vs. HA, and the rates of mortality and loss to follow-up. Because some of these inputs are expected to change over the two year period of follow-up, the expected number of person-years of follow-up and the expected numbers of study events in each group were calculated, initially for the first year of follow-up; the calculation was then repeated for the second year of follow-up, after having estimated the number of patients in each group who would survive, be event-free, and available for continued follow-up between 12 and 24 months post-randomization.

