For the secondary outcomes, an important difference in SF-12 is considered to correspond to a moderate effect as reported by Cohen (Cohen, 1988) as well as a minimally important difference in the SF-12 as reported by Ware (Ware & Sherbourne, 1992). In both cases, the value is at least half the standard deviation, equivalent to 4-point difference in score. Specifying an alpha level=0.05, a beta=0.20 (study power=80) and a standard deviation of 8 (Jaglal et al, 2000), a sample of at least 128 patients (64 per group) is required to ensure detection of a half standard deviation improvement. In clinical drug trials, a 9-point change in WOMAC functional score was accepted as a minimally significant improvement in symptoms (Turbach et al, 2005). In this study, at least 90 patients (45 per group) would be required to detect this difference (alpha level=0.05, beta=0.20,  $\sigma = 15$ ). Previous studies have found a standard deviation of 0.20 for the EQ-5D (Tidermark et al, 2003). To detect a difference of 0.10 (half the standard deviation) with 80% power at an alpha level of 0.05, this study requires a total of 128 patients (64 per group). Thus, in all circumstances, the desired sample size of **1,434 patients** will be sufficient to detect clinically meaningful differences in the secondary measures of outcome.

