| Functional Outcomes and Quality of Life | 
Functional outcome and quality of life were measured using self-administered and interview-administered questionnaires. Functional outcome questionnaires included a generic health status measurement instrument (SF-12), a hip function and pain questionnaire (WOMAC), a health outcome measure (EQ-5D), and a functional mobility test (TUG).
 
The SF-12 Health Survey is a standardized instrument to measure health-related quality of life. This self-administered, 12-item questionnaire covers eight main health domains that make up the Physical and Mental Health Composite Scores (PCS & MCS). Each domain consists of one or two questions and is scored separately from 0 (lowest level) to 100 (highest level).
 
The WOMAC is a self-administered questionnaire that assesses the three dimensions of pain, disability and joint stiffness in knee and hip osteoarthritis, and consists of 24 questions. This questionnaire uses a Likert scale, consisting of responses including: none, mild, moderate, severe, and extreme. Specifically, for the WOMAC questionnaire, the Likert scale is in reverse order. Therefore, a higher score indicates worse pain, stiffness, and functional limitations. The ranges for each dimension are: 0-20 for pain, 0-8 for stiffness, and 0-68 for physical function.²
 
The EQ-5D is a standardized instrument that measures quality of life in five dimensions (mobility, self-care, usual activities, pain/discomfort, and anxiety/depression). Each dimension has three response options: 1=no problems, 2=some problems, and 3=extreme problems. Each response corresponds with a one-digit number that can then be combined into a 5-digit number to describe the participant's state of health. The participant's state of health is then translated into a corresponding utility score.² The EQ-5D also includes a visual analogue scale (VAS) that assesses the individual's health today on a scale from 0-100, with the endpoints being 'worst imaginable state of health' and 'best imaginable state of health'.^{3,4}
 
The TUG test is a standardized, physical test to assess balance and mobility in the participants. The participant is timed while they perform simple physical movements, such as rising from an arm chair, walking 10 feet, walking back to the chair, and sitting down. A faster time indicates that the participant has greater functional performance, while a lower score may identify participants who are at risk for increased falls in the community.⁵
 
The SF-12, WOMAC, and EQ-5D were asked at 10 weeks, 6, 9, 12, 18, and 24-month visits. The TUG was performed at 1 and 10-week 6, 12, and 24-month visits.
 |

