Cox proportional hazards modeling was used to estimate the relative effect of THA versus HA on time to mortality, serious adverse events, and hip-related complications, separately, and included the same independent variables as listed for the primary analysis as well as including surgeon as a random effect. The hip-related complications analysis was a competing risk analysis with death as the competing risk. The estimates from the competing risk analysis for clustered data analyses were marginal estimates. We report the HRs and 99% CIs for the proportional hazards models. We performed proportional hazards regressions only for hip-related complications in which there were at least 50 events. Using multi-level models, the effect of THA versus HA on quality of life (SF-12, EQ-5D), function (WOMAC), and mobility (TUG) were estimated separately. Randomized treatment, visit (entered as a categorical variable) were also included as independent variables. Because we believed that the effect of THA versus HA may change over time, we also included an interaction term between treatment and visit. When the interaction term between treatment and visit was not statistically significant at $\alpha=0.05$, we removed it from the model. When the interaction term was significant, we reported the treatment effect at each visit. We accounted for death via joint modelling, using the method described by Rizopoulos.⁷ The SF-12, WOMAC, and EQ-5D were summarized using mean difference (MD) and 99% CIs. We analyzed the TUG as a dichotomous outcome with the following categories: a) patients who complete the test in ≤ 12 seconds, and b) those who require >12 seconds to complete the test or were unable to complete the test. We selected 12 seconds as the cut-off because this was the threshold used by the Centers for Disease Control and Prevention.⁸ The TUG was summarized using odds ratios and 99% CIs. For our multi-level analyses of quality of life, function, and mobility, all available data were used with no imputation performed. The models do not require that a patient have valid scores at all follow-up visits. We chose alpha levels of 0.05 and 0.01 for the primary and secondary outcomes, respectively. When scoring the WOMAC domains, we used the mean of the items that were answered in our calculation if at least 4 of the 5 pain items were answered, at least 1 of the 2 stiffness items were answered, and if at least 14 of the 17 function items were answered. If there were less items answered, the domain was set to missing. To calculate the WOMAC total score, we required non-missing scores for all 3 domains.

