2.11 Interpretation of Blinded Data

Hypothesis: We hypothesize that THA will have similar or lower rates of secondary procedures and higher functional outcome scores at 24 months compared with HA.

Here, we present alternative interpretations of blinded preliminary results. Blinded data interpretation may decrease the frequency of misleading data interpretation. Widespread adoption of blinded data interpretation with a minimum set of recommendations should be widely adopted.¹⁰

Secondary procedures over two years did not differ between treatment groups X and Y. The Kaplan Meier curve for the primary outcome suggests that the hazard ratios (HRs) remain constant up to 1 year (HR=1.30, 95% CI 0.86-1.95, $p=0.217$; non-significant estimates favoring treatment Y) and suggested estimates favouring treatment X after 1 year (up to 2 years) (HR=0.24, 95% CI 0.08-0.73; $p=0.011$).

Deaths did not differ between treatment groups X and Y over a 2-year period ($p=0.493$).

Serious adverse events ($p=0.052$) and hip-related complications ($p=0.277$) between treatment groups X and Y did not differ over a 2-year period.

Treatment X demonstrated significantly better overall WOMAC and EQ-5D utility scores ($p<0.05$) compared to Treatment Y (and trended towards better SF-12 PCS scores) over a 2-year period. TUG scores (cut-off 12 seconds) did not differ between treatment groups ($p=0.181$).

Subgroup analyses did not show any differences in the treatment effect between different subgroups ($p>0.05$).

Given the above preliminary findings, the more plausible hypothesis follows. Treatment X is THA and Treatment Y is HA. THA does not result in a statistically significant difference in secondary procedure rates over a 2-year period compared to HA; however, our findings suggest THA may have more secondary procedures earlier (less than 1 year, possibly driven by higher dislocations *results still blinded*) and HA may have more secondary procedures after 1-year post-fracture in those who did not have a secondary procedure during the first year. Functional outcome scores over 2 years favour THA compared to HA. These differences in function are small (although statistically significant). A lack of difference in secondary procedures, hip-related complications, and deaths, a lack of subgroup effects, and modest improvements in function render THA mildly superior to HA over 2 years. It's not unreasonable to consider the two treatments similar given

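### SAP 2.11 labels one treatment mildly superior on function from p<0.05 and a description of small, without using the clinically meaningful differences in Protocol 7.1

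*SAP*

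**What the plan says.** **Protocol 7.1** names a difference for three of the functional and quality-of-life measures: 4 points on SF-12 (SD 8), 0.10 on EQ-5D (SD 0.20) and, for WOMAC (SD 15), "a 9-point change in WOMAC functional score was accepted as a minimally significant improvement in symptoms". It closes by calling these, together, clinically meaningful differences. It also sets the error rates: "Alpha levels of 0.05 for the primary and 0.01 for the secondary outcomes were chosen".

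**SAP 2.6** gives the WOMAC domain ranges as "0-20 for pain, 0-8 for stiffness, and 0-68 for physical function".

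**SAP 2.8** repeats the error rates ("We chose alpha levels of 0.05 and 0.01 for the primary and secondary outcomes, respectively") and plans mean differences with 99% confidence intervals for SF-12, WOMAC and EQ-5D. It says nothing about what size of difference would matter.

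**SAP 2.11** reports, still blinded, that treatment X was significantly better at p<0.05 on overall WOMAC and EQ-5D utility, that the SF-12 physical score only trended, and that the functional differences are small. If X is THA it concludes: "modest improvements in function render THA mildly superior to HA over 2 years". If X is HA it gives the same verdict with the labels exchanged. In both scenarios the next sentence says the treatments may reasonably be considered similar.

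**The concern.** A blinded interpretation is meant to settle the reading of the results before anyone knows which arm is which. Here the functional part allows two readings of the same data, mild superiority and similarity, and gives no criterion for choosing between them. Small and modest are tied to no number, although the protocol contains numbers that could serve.

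Two further points weaken the label:

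- The p<0.05 behind it is looser than the plan's own 0.01 level for secondary outcomes.
- The WOMAC result is for the overall score, whereas the protocol's only WOMAC value belongs to the function score.

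Function is the only item in the verdict sentence that favours either arm. The other items are absences of difference. Higher functional scores with THA are also part of the trial's stated hypothesis, so this wording matters although the outcomes are secondary.

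**Working it through.** **Step 1: reproduce the protocol's own figures.** For two means with equal arms, n per group = 2 × (1.96 + 0.842)² × (SD/d)², at two-sided alpha 0.05 and 80% power.

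- SF-12: 2 × 7.85 × (8/4)² = 62.8, so 63 per group, 126 in total.
- WOMAC function: 2 × 7.85 × (15/9)² = 43.6, so 44 per group, 88 in total.
- EQ-5D: 2 × 7.85 × (0.20/0.10)² = 62.8, so 63 per group, 126 in total.

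The noncentral t version gives 128, 90 and 128, exactly as Protocol 7.1 states. The SDs and differences have therefore been read correctly.

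**Step 2: patients with scores at 24 months.** Protocol 7.1 assumes 15% mortality and 5% loss in each of two years: 1,434 × 0.80² = 917. Multiplying the two rates instead gives 1,434 × (0.85 × 0.95)² = 935. Patients who have had a secondary procedure remain in functional follow-up, so the event-free fractions in Protocol 7.1 are not the right ones here.

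**Step 3: smallest difference that reaches significance at one visit.** Difference = z × SD × √(4/N), with √(4/917) = 0.0660.

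| Measure | Protocol value | Alpha 0.01 (z = 2.576) | Share | Alpha 0.05 (z = 1.96) | Share |
|---|---|---|---|---|---|
| SF-12 | 4 | 1.36 | 34% | 1.04 | 26% |
| WOMAC function | 9 | 2.55 | 28% | 1.94 | 22% |
| EQ-5D | 0.10 | 0.034 | 34% | 0.026 | 26% |

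**Step 4: sensitivity.**

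- With all 1,434 patients the shares are 23% to 27% at alpha 0.01 and 17% to 21% at 0.05.
- With half of them (717) they are 32% to 38% and 24% to 29%.
- The protocol's 9% allowance for surgeon effects multiplies each share by √1.09 = 1.04.
- The WOMAC share does not depend on the scale, provided the 9 points and the SD of 15 lie on the same one.

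**Step 5: what this means for the label.** At N = 917 the half-width of a 99% interval equals the alpha 0.01 column above. An observed difference can therefore be significant at 0.01 while its whole 99% interval lies inside plus and minus the protocol's value:

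- WOMAC function: from 2.55 to 9 − 2.55 = 6.45 points.
- EQ-5D: from 0.034 to 0.10 − 0.034 = 0.066.
- SF-12: from 1.36 to 4 − 1.36 = 2.64 points.

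**Step 6: the WOMAC score.** The SAP's domains sum to 20 + 8 + 68 = 96, and SAP 2.9 refers to a total-score model. The 9 points belong to function, and the protocol does not state their scale. On 0-68 they are 9 points. If they came from a 0-100 scale they would be 9 × 68/100 = 6.1 points on 0-68. No threshold is given for the total.

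**The case against.** **The text does weigh size.** A reader might infer that superiority is declared from significance alone. That goes too far. SAP 2.11 calls the effects small and modest, weighs procedures, complications, deaths and subgroups, accepts that the treatments may be similar, and doubts that THA should be the implant of choice. What stands is that size is judged without a number.

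**No threshold is shown to be missed.** A reader might also infer that the observed differences were clinically trivial. The documents do not support this, because SAP 2.11 gives no mean difference or interval. It is also a two-way reading of blinded preliminary results, not the trial's final conclusion. The SF-12 physical score only trended, so the label rests on WOMAC and EQ-5D.

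**The protocol's values are sample-size inputs.** This is fair. The EQ-5D figure is half a standard deviation, and the WOMAC figure is a change accepted in drug trials, not a between-arm margin. Still, they are the only values in the documents described as clinically meaningful, and they were set for these outcomes. A rule added now would follow a look at blinded results, which should be stated.

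**The trial looks oversized for these outcomes.** One might set 1,434 against the protocol's 90 to 128 and speak of a tenfold excess. Those needs are at alpha 0.05. At the plan's 0.01 they are 134 to 192 by noncentral t, so 917 patients is about five to seven times the need.

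**The hypothesis seems to point the wrong way.** It predicts "similar or lower rates of secondary procedures and higher functional outcome scores at 24 months compared with HA", while for WOMAC SAP 2.6 says: "Therefore, a higher score indicates worse pain, stiffness, and functional limitations". This is a matter of wording. "All statistical hypotheses will be two-sided", SAP 2.11 speaks of better scores, and TUG is analysed as a dichotomy, so no analysis changes.

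**Conclusion.** The point holds as one of interpretation. SAP 2.11 attaches a superiority label to functional results described only as p<0.05 and small, and allows the opposite reading in the next sentence. It does not use the protocol's differences or the plan's own 0.01 level. In a trial of this size significance does not show an important benefit: it is reached at about 28% (WOMAC function) to 34% (SF-12, EQ-5D) of the protocol's values at alpha 0.01, and at about 22% to 26% at 0.05. The WOMAC result is also judged on a score for which no threshold is set.

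The figures assume equal arms, the protocol's SDs, its attrition rates, a single-visit comparison and no clustering. The planned multi-level joint model could be more or less precise. Whether the observed differences reached the protocol's values cannot be told from the documents.

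**What to change.** In SAP 2.8 and 2.11:

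1. Base the functional conclusion on the mean difference and the 99% interval already planned, set against the Protocol 7.1 values (SF-12 4, WOMAC function 9, EQ-5D 0.10).
2. Judge WOMAC on the function domain and state the scale of the 9 points, or state and justify a threshold for the total score.
3. Where the 99% interval lies wholly inside plus and minus the threshold, report no important difference in place of the mild-superiority wording. Otherwise report the estimate and interval against the threshold, without a superiority label based on p<0.05.
4. State that this rule was added after the blinded results had been seen, and that the thresholds come from the protocol.

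The cost is wording: SAP 2.8 already plans the mean differences and 99% intervals, and no new data are needed. If the function domain has not been modelled separately, that is one further run of the same model. The downside is that a small but real functional benefit would no longer be called superiority.
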